Screening will occur within 28 days of the first dose of study medication. All participants will provide informed consent and undergo Screening evaluations to determine their eligibility. For individual participants, the total duration of participation from the Screening Visit to the Follow-up Contact will be a minimum of approximately 5 weeks and a maximum of approximately 10 weeks.

Data Monitoring Committee: No

Statistical Methods

[figure not shown]
Linear regression will be used to characterize the potential relationship between appropriate PK parameters (CL/F, CL_u/F and CL_r) for PF-06882961 and renal function (eGFR).

A one-way analysis of variance (ANOVA) will be used to compare the natural log transformed AUC_{inf} (if data permit), AUC_{last} , C_{max} and fu of PF-06882961 for each of the T2DM renal impairment groups (Test, Groups 3, 4, 5) to the T2DM normal renal function group (Reference, Group 2). Also, the T2DM normal renal function group (Test, Group 2) will be compared to the healthy normal renal function group (Reference, Group 1). The ANOVA model will include all groups (ie, both T2DM and healthy participants from the 5 groups). Estimates of the adjusted mean differences (Test-Reference) and corresponding 90% confidence intervals (CIs) will be obtained from the model. The adjusted mean differences and 90% CIs for the differences will be exponentiated to provide estimates of the ratio of adjusted geometric means (Test/Reference) and corresponding 90% CIs. If substantial differences in demographic characteristics between healthy (Group 1), T2DM normal (Group 2) and T2DM renal impairment function participants (Groups 3, 4, 5) are observed, covariates such as weight and age may be explored.

The PK parameters for PF-06882961 will also be summarized descriptively by renal function group and population (healthy vs. T2DM).

For summary statistics and median/mean plots by sampling time, the nominal PK sampling time will be used. For individual participant plots by time, the actual PK sampling time will be used.

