3. OBJECTIVES AND ENDPOINTS

Objectives	Endpoints
Primary:	Primary:

To compare the PK of PF-06882961 following administration of a single oral dose in adult participants with T2DM and varying degrees of renal impairment relative to T2DM participants without renal impairment.	
Plasma: C_{max}, AUC_{inf}, AUC_{last}, fu, as data permit.
Secondary:	Secondary:

To compare additional PK parameters of PF-06882961 following administration of a single oral dose in adult participants with T2DM and varying degrees of renal impairment relative to T2DM participants without renal impairment.To evaluate the safety and tolerability of a single oral dose of PF-06882961 in T2DM participants with varying degrees of renal impairment and in participants with normal renal function.	
Plasma: $C_{max,u}$, $AUC_{inf,u}$, $AUC_{last,u}$, CL/F, CL_u/F, V_z/F, $V_{z,u}/F$, T_{max}, $t_{1/2}$, as data permit.Incidence and severity of treatment-emergent AEs, clinical laboratory abnormalities, vital signs (blood pressure and pulse rate), ECG parameters (heart rate, QT, QTcF, PR and QRS intervals).
Tertiary/Exploratory:	Tertiary/Exploratory:

To compare urine PK parameters of PF-06882961 following administration of a single oral dose in adult participants with T2DM and varying degrees of renal impairment relative to T2DM participants without renal impairment.To compare the PK of PF-06882961 following administration of a single oral dose in adult participants with T2DM and normal renal function relative to healthy participants with normal renal function.To explore the relationship of markers of innate OATP activity in adult participants with T2DM and varying degrees of renal impairment relative to participants with normal renal function.To enable exploratory research through collection of banked biospecimens, unless prohibited by local regulations or ethics committee decision.	
Urine: CL_r, Ae_{24}, $Ae_{24}\%$.Plasma: C_{max}, T_{max}, AUC_{inf}, AUC_{last}, CL/F, V_z/F, $t_{1/2}$, fu, as data permit;Urine: CL_r, Ae_{24}, $Ae_{24}\%$.CP-I concentration.Potential results from exploratory analysis of banked biospecimens (these results may or may not be generated in the context of the present study).

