9.4.3.1.3. Statistical Methods

Linear regression will be used to characterize the potential relationship between appropriate PK parameters (CL/F, CL_u/F and CL_r) for PF-06882961 and renal function (eGFR). eGFR values obtained on Day 1 and only participants from the T2DM groups (Groups 2 to 5) will be included in the regression analysis. Estimates of the slope and intercept, together with their precision (90% CIs), and the coefficient of determination will be obtained from the model. The effect of covariates such as weight, gender, and age may be explored, and details will be provided in the SAP.

A one-way analysis of variance (ANOVA) will be used to compare the natural log transformed AUC_{inf} (if data permit), AUC_{last}, C_{max}, fu, AUC_{inf,u} (if data permit), AUC_{last,u} and C_{max,u} of PF-06882961 for each of the T2DM renal impairment groups (Test, Groups 3, 4, 5) to the T2DM normal renal function group (Reference, Group 2). Also, the T2DM normal renal function group (Test, Group 2) will be compared to the healthy normal renal group (Reference, Group 1). The ANOVA model will include all groups (ie, both T2DM and healthy participants from the 5 groups). Estimates of the adjusted mean differences (Test-Reference) and corresponding 90% CIs will be obtained from the model. The adjusted mean differences and 90% CIs for the differences will be exponentiated to provide estimates of the ratio of adjusted geometric means (Test/Reference) and corresponding 90% CIs. If substantial differences in demographic characteristics between healthy (Group 1), T2DM normal (Group 2) and T2DM renal impairment function participants (Groups 3, 4, 5) are observed, covariates such as weight, gender, and age may be explored.

The PK parameters for PF-06882961 will also be summarized descriptively by renal function group and population (healthy vs. T2DM). Box and whisker plots for individual PK parameters (AUC_{inf}, AUC_{last}, C_{max}, fu, AUC_{inf,u}, AUC_{last,u} and C_{max,u}) will be constructed by renal function group and population and overlaid with geometric means.

For summary statistics and median or mean plots by sampling time, the nominal PK sampling time will be used. For individual participant plots by time, the actual PK sampling time will be used.

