3.2. Secondary Endpoint(s)

3.2.1. Additional Plasma PK parameters of PF-06882961

- $C_{max,u}$, $AUC_{inf,u}$, $AUC_{last,u}$, CL/F , CL_u/F , V_z/F , $V_{z,u}/F$, T_{max} , $t_{1/2}$, as data permit

The plasma PK parameters for PF-06882961 in Table 4 will be determined using standard non-compartmental methods:

Table 4. Summary of Additional Plasma PK parameters of PF-06882961 to be calculated

Parameter	Analysis Scale	PF-06882961 20mg
CL/F^*	ln	A, D
V_z/F^*	ln	D
T_{max}	R	D
$t_{1/2}^*$	R	D

*=if data permits. Abbreviations: A = analyzed using a statistical model; D=displayed with descriptive statistics as outlined in [Table 8](#) in Section [6.2.1](#); ln=natural-log transformed; R=raw (untransformed).

The plasma PK parameters for unbound PF-06882961 will be calculated as described in Table 5:

Table 5. Summary of Plasma PK parameters of Unbound PF-06882961 to be calculated

Parameter	Method of Determination	Analysis Scale	PF-06882961 20 mg
$AUC_{last,u}$	$fu \times AUC_{last}$	ln	D
$AUC_{inf,u}^*$	$fu \times AUC_{inf}$	ln	D
$C_{max,u}$	$fu \times C_{max}$	ln	D
CL_u/F^*	$Dose/(AUC_{inf,u})$	ln	A, D
$V_{z,u}/F^*$	$Dose/(AUC_{inf,u} \times k_{el})$	ln	D

*=if data permits. Abbreviations: A = analyzed using a statistical model, D=displayed with descriptive statistics as outlined in [Table 8](#) in Section [6.2.1](#); ln=natural-log transformed, R=raw (untransformed).

For the linear regression analysis assessing the relationship between CL/F , CL_u/F and CL_r and eGFR, the primary equation for eGFR will be SCr-based:

CKD-Epi equation⁽¹⁾: $eGFR \text{ (mL/min/1.73m}^2\text{)} = 141 \times \min(\text{SCr } / \kappa, 1)^\alpha \times \max(\text{SCr } / \kappa, 1)^{-1.209} \times 0.993^{\text{Age}} \times 1.018 \text{ [if female]} \times 1.159 \text{ [if Black]}$

where:

- SCr is serum creatinine in mg/dL (based on the standardized assay)
- κ is 0.7 for females and 0.9 for males
- α is -0.329 for females and -0.411 for males
- min indicates the minimum of SCr / κ or 1
- max indicates the maximum of SCr / κ or 1
- Age is in years

Additional outputs will also be produced using the following alternative equations to calculate eGFR:

Cockcroft-Gault (CG)⁽²⁾: eGFR (ml/min/1.73 m²) = [(140-Age) \times Weight \times 0.85 if female]/(72 \times SCr)

Modification of Diet in Renal Disease (MDRD)⁽³⁾: eGFR (ml/min/1.73 m²) = 175 \times (SCr)^{-1.154} \times (Age)^{-0.203} \times (0.742 if female) \times (1.212 if black)

where:

- Age is in years
- Weight is in kg

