5.2.3. One-way Analysis of Variance (ANOVA)

The *ANOVA* model will include all groups (i.e. both T2DM and healthy participants from the 5 groups) as a factor.

Estimates of the adjusted mean differences (Test-Reference) and corresponding 90% CIs will be obtained from the model. The adjusted mean differences and 90% CIs for the differences will be exponentiated to provide estimates of the ratio of adjusted geometric means (Test/Reference) and corresponding 90% CIs. Example SAS code is given in [Appendix 1](#).

Potential differences in demographic characteristics between healthy (Group 1), T2DM normal (Group 2) and T2DM renal impairment function participants (Groups 3, 4, 5) and their impact on study conclusions will be explored based on consideration of the covariates weight, gender and age. This will be implemented by utilizing a stepwise linear regression approach, with model selection using Akaike's Information Criterion [AIC]). All the above covariates and factors will be considered (group as a factor will be restricted to always remain in the model) and if the final model selected includes at least one of these additional covariates/factors, this additional model will be reported in addition to the main ANOVA model above. Example SAS code is given in [Appendix 1](#).

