6.1. Primary Endpoint(s)

6.1.1. C_{\max} , AUC_{inf} , AUC_{last} , fu for PF-06882961

6.1.1.1. Main Analysis

C_{\max} , AUC_{inf} (if data permit), AUC_{last} and fu will be listed, summarized descriptively and analyzed by group for participants in the PK parameter set (as defined in Section 4). Missing values will be handled as detailed in Section 5.3.1.

Linear regression will be used to characterize the potential relationship between appropriate PK parameters (CL/F , CL_u/F and CL_r) for PF-06882961 and renal function (eGFR as obtained on Day 1 and defined by the SCr-based CKD-Epi equation in Section 3.2.1), as described in Section 5.2.4, where the PK parameter will be the dependent variable in the separate models.

Plots of PK parameters (CL/F , CL_u/F and CL_r) for PF-06882961 versus renal function (eGFR as obtained on Day 1 and defined by the SCr-based CKD-Epi equation in Section 3.2.1) will be constructed. A regression line and 90% confidence region for the PK parameters and eGFR will be included if appropriate. Vertical lines for the renal function group cut-off values will also be presented on the plots. Different symbols will be used to identify participants from different renal function groups.

For exploratory purposes, these analyses and figures will additionally be carried out separately for each of the alternative two methods for calculating eGFR, as defined in Section 3.2.1.

A one-way analysis of variance (ANOVA) described in Section 5.2.3, that includes all 5 groups in the same model, will be used to compare the natural log transformed of C_{\max} , AUC_{inf} , AUC_{last} and fu of PF-06882961 separately, for each of the T2DM renal impairment groups (Test, Groups 3, 4, 5) to the T2DM normal renal function group (Reference, Group 2). Also, the T2DM normal renal function group (Test, Group 2) will be compared to the healthy normal renal group (Reference, Group 1).

For summary statistics and median or mean plots by sampling time, the nominal PK sampling time will be used. For individual participant plots by time, the actual PK sampling time will be used. The plasma PK parameters of PF-06882961 for each group will be summarized as specified in Table 7 below.

Table 7. Summary statistics to be produced for Plasma PK Parameters of PF-06882961

Parameter	Summary Statistics
-----------	--------------------

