6.2. Secondary Endpoint(s)

6.2.1. Additional Plasma PK parameters of PF-06882961

$C_{\max,u}$, $AUC_{\text{inf},u}$, $AUC_{\text{last},u}$, CL/F , CL_u/F , V_z/F , $V_{z,u}/F$, T_{\max} , $t_{1/2}$ will be listed, summarized descriptively and analyzed by group in the PK parameter set (as defined in Section 4). Missing values will be handled as detailed in Section 5.3.

The additional plasma PK parameters of PF-06882961 for each group will be summarized as specified in Table 8 below.

Table 8. Summary statistics to be produced for Additional Plasma PK Parameters of PF-06882961

Parameter	Summary Statistics
$C_{\max,u}$, $AUC_{\text{inf},u}$, $AUC_{\text{last},u}$, CL/F , CL_u/F , V_z/F , $V_{z,u}/F$	N, arithmetic mean, median, $cv\%$, standard deviation, minimum, maximum, geometric mean and geometric $cv\%$.
T_{\max}	N, median, minimum, maximum.
$t_{1/2}$	N, arithmetic mean, median, $cv\%$, standard deviation, minimum, maximum.

The following plot will be presented:

- Box and whisker plots for individual PK parameters ($AUC_{\text{inf},u}$, $AUC_{\text{last},u}$ and $C_{\max,u}$) will be constructed by group and overlaid with geometric means.

The following summaries will additionally be presented for the plasma concentration data of PF-06882961 using the PK Concentration Set (as defined in Section 4):

- a listing of all concentrations sorted by participant ID and nominal time post-dose for each group. The concentration listing will also include the actual times. Deviations from the nominal time will be given in a separate listing.

- a summary of concentrations for each nominal time post-dose (produced separately for each group), where the set of statistics will include n, mean, median, standard deviation, coefficient of variation (cv), minimum, maximum and the number of concentrations above the lower limit of quantification.
- median concentration time plots (on both linear and semi-log scales) against nominal time post-dose by group in the same plot.
- individual concentration time plots by group (on both linear and semi-log scales) against actual time post-dose (there will be separate spaghetti plots for each group, with a line for each participant, per scale).

The nominal PK sampling time will be used for summary statistics and relevant median plots, whereas for individual participant plots by time, the actual PK sampling time will be used.

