6.3.2. CP-I concentration

CP-I will be summarized descriptively by group and overall for participants in the CP-I concentration set (as defined in Section 4). Missing values will be handled as detailed in Section 5.3.

Linear regression will be used to characterize the potential relationship between appropriate PK parameters (AUC_{inf} [as data permit], $AUC_{inf,u}$ [as data permit], AUC_{last} , $AUC_{last,u}$, CL/F and $CL_{u/F}$) for PF-06882961 versus innate OATP activity (as measured by CP-I on Day 1) as described in Section 5.2.4, where the PK parameter will be the dependent variable in the separate models and CP-I will be the explanatory variable. This will be applied to participants from the T2DM groups only.

Plots of PK parameters vs. CP-I will be constructed separately for each PK parameter. A regression line and 90% confidence region for the PK parameters will be included in the plots and different symbols will be used to identify participants from different renal function groups.

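### The SAP drops the ANOVA ratios and 90% CIs for unbound exposure that the protocol plans, without a reason, and its own entries for these parameters conflict

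*SAP*

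**What the plan says.** Protocol 9.4.3.1.3 lists the ANOVA parameters as AUCinf, AUClast, Cmax, fu, AUCinf,u, "AUC_{last,u} and C_{max,u} of PF-06882961 for each of the T2DM renal impairment groups", with AUCinf and AUCinf,u subject to data permitting. Groups 3, 4 and 5 are each compared with Group 2, and Group 2 with Group 1. The differences and 90% CIs are exponentiated to ratios.

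The protocol synopsis stops earlier: its list ends with "and fu of PF-06882961 for each of the T2DM renal impairment groups" and names no unbound exposure.

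SAP 6.1.1.1 names the same four parameters as the synopsis, running the ANOVA on the "natural log transformed of C_{\max} , AUC_{inf} , AUC_{last} and fu of PF-06882961 separately". The three unbound exposures appear elsewhere in the SAP:

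- **Table 5 (SAP 3.2.1)** gives them the natural-log scale and code D only. The code key in that section reads "A = analyzed using a statistical model; D=displayed with descriptive statistics". In the same table CLu/F is coded A, D.
- **SAP 6.2.1** says that they, with the other secondary plasma parameters, "will be listed, summarized descriptively and analyzed by group in the PK parameter set". It names no model. What follows for them is Table 8 (descriptive statistics) and box plots.
- **SAP 6.3.2** regresses AUCinf,u and AUClast,u on CP-I, "where the PK parameter will be the dependent variable in the separate models and CP-I will be the explanatory variable".

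The unbound exposures are secondary endpoints in Protocol Section 3, under the objective "To compare additional PK parameters of PF-06882961 following administration of a single oral dose in adult participants with T2DM" and varying renal impairment relative to T2DM without it.

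**The concern.** A programmer who follows SAP 6.1.1.1 and Table 5 will produce no group ratio and no CI for unbound exposure. One who follows the protocol, or who takes the wording of SAP 6.2.1 to mean an ANOVA, will produce both. The SAP does not settle which is meant and gives no reason for the shorter list.

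Protocol 4.2 describes the drug as highly protein bound and has fu measured in each participant to see how binding changes with renal impairment. If binding changes, total exposure and unbound exposure can give different pictures of the renal effect. Protocol 2.3 says the results will feed into dosing recommendations in renal impairment. The unbound group comparison with its interval is therefore a result that readers will look for, and the protocol planned it.

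**Working it through.** **1. The entries side by side**

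| Place | AUCinf, AUClast, Cmax, fu | AUCinf,u, AUClast,u | Cmax,u |
|---|---|---|---|
| Protocol 9.4.3.1.3 | ANOVA | ANOVA | ANOVA |
| Protocol synopsis | ANOVA | not listed | not listed |
| SAP Tables 3 and 5 | A, D | D | D |
| SAP 6.1.1.1 | ANOVA | not listed | not listed |
| SAP 6.2.1 | not covered | analysed by group, no model | analysed by group, no model |
| SAP 6.3.2 | AUCinf, AUClast regressed on CP-I | regressed on CP-I | not listed |

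No SAP entry assigns the unbound exposures to the ANOVA. Code D conflicts with 6.2.1 for all three and with 6.3.2 for the two AUCs.

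**2. Count of planned ratios with 90% CIs**

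- Comparisons per parameter: 3 (Groups 3, 4, 5 vs 2) + 1 (Group 2 vs 1) = 4.
- Protocol 9.4.3.1.3: 7 × 4 = 28. SAP: 4 × 4 = 16. Missing: 28 − 16 = 12.
- Of these, 3 × 3 = 9 are renal comparisons under the secondary objective, and 3 are Group 2 vs Group 1.

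**3. The plan's own precision figure**

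Protocol 9.2 gives a half-width of ±0.490 for total AUCinf or Cmax, with SD 0.489, 8 per group and 80% coverage probability. The formula is

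half-width = t(0.95, df) × SD × √(χ²(0.80, df)/df) × √(1/8 + 1/8).

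With df = 14 this gives 0.4903, so the figure reproduces. With the pooled five-group df = 35 it is 0.451. The finding does not dispute these figures.

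**4. Can the missing results be obtained from planned output?**

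*From the total-exposure and fu ANOVAs.* Each unbound exposure is fu times the total exposure. On the log scale the unbound ratio is therefore the total-exposure ratio times the fu ratio, provided the same participants contribute to both. The CI does not follow, because

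Var(ln unbound) = Var(ln total) + Var(ln fu) + 2 Cov(ln total, ln fu),

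and the covariance is not reported. The documents give no SD for fu. Assuming an SD of ln fu from 0 to 0.3 and a correlation from −0.5 to +0.5, the df = 35 half-width runs from 0.39 to 0.64. The two separate intervals do not pin it down.

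*From SAP Table 8.* It gives N, geometric mean and geometric CV% by group. With SD² = ln(1 + CV²) in each group, the ANOVA error variance is Σ(nᵢ − 1) ln(1 + CVᵢ²) / Σ(nᵢ − 1). On simulated data this equalled the ANOVA mean square exactly (0.2204 both ways). Rounding CV to a whole percent matters little: CVs of 51.5% and 52.5% give SD = √ln(1.2652) = 0.485 and √ln(1.2756) = 0.493. The unadjusted ratio and CI can therefore be rebuilt by hand.

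*Covariate-adjusted model.* When the AIC selection in SAP 5.2.3 retains weight, gender or age, "this additional model will be reported in addition to the main ANOVA model above". Group summaries cannot supply that model, because it needs participant-level values.

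*From the regressions.* Since CLu/F = Dose/AUCinf,u at a fixed 20 mg, ln CLu/F = ln(20) − ln AUCinf,u. The CLu/F regression on eGFR is thus the ln AUCinf,u regression with the slope sign reversed. Neither it nor the CP-I regressions gives a group ratio, and neither covers Cmax,u.

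**The case against.** The strongest reply is that little is lost and nothing is broken. Protocol Section 9 and SAP Section 2 both let the SAP modify the protocol, and only major changes to the primary endpoints or their analyses require an amendment. These endpoints are secondary, and no hypothesis test or decision rule depends on them. The SAP matches the synopsis. The point estimates follow from planned ratios and the unadjusted CIs from Table 8. SAP 6.2.1 also lists the individual parameter values, so the adjusted model could be refitted afterwards with the demographic data. That model is itself conditional on the AIC selection. A secondary objective to compare parameters does not by itself require an ANOVA: Vz/F, Tmax and t½ fall under the same objective and Protocol 9.4.3.1.3 does not put them in the ANOVA. The wording in SAP 6.2.1 also covers Tmax and t½, both coded D, so it may be template text.

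Most of this stands, and it limits the weight of the point. There is no breach and the data are not lost. The three Group 2 vs Group 1 ratios serve no listed endpoint, because the exploratory objective for that comparison names no unbound exposure.

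It does not remove the point. The protocol did name these three parameters for the ANOVA, and the SAP neither says they were removed nor explains it. A hand calculation or later refit is not a prespecified result. If the wording of 6.2.1 is template text, it should be corrected. If it means an ANOVA, Table 5 is wrong.

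**Conclusion.** The concern holds. Followed as written, the SAP leaves out 12 of the protocol's 28 ANOVA ratios with 90% CIs, 9 of them under the secondary objective, and its entries for the unbound exposures contradict each other. The count follows directly from the parameter and group lists and rests on no assumption. The conclusion that the unadjusted results are recoverable relies on Table 8 being reported for every group. The range of half-widths depends on assumed values for fu. The point should be fixed before database lock, but it does not threaten the primary analysis.

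**What to change.** In SAP Table 5, code AUClast,u, AUCinf,u and Cmax,u as A, D. In SAP 6.2.1, state that the ANOVA of Section 5.2.3 is applied to their natural logs (AUCinf,u if data permit) for Groups 3, 4 and 5 vs Group 2 and for Group 2 vs Group 1, as in Protocol 9.4.3.1.3. Bring the protocol synopsis into line with that section; this can wait for the next amendment, since the SAP change restores the analysis on its own.

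If the removal was intended, the SAP should say so, give the reason, and delete the statement in 6.2.1 that these parameters are analysed by group.

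The cost is a few lines of text and three more runs of a model already programmed. No new data and no change in sample size are needed.
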